4.9. Secondary Outcomes

Secondary objectives are to evaluate:

1. Number of recurrent shoulder dislocations up to 24 months post-treatment;
2. Symptoms of instability up to 24 months post-treatment;
3. Patient reported outcomes include the WOSI Index, ASES score, Shoulder Activity Scale, EQ-5D, VAS pain scale and Patient Satisfaction questionnaire.

- The WOSI is a self-administered quality of life outcome measure designed for clinical trials evaluating treatments for patients with shoulder instability. It has been shown to have high reliability, validity and responsiveness¹¹. The WOSI score is commonly utilized and has been shown to provide excellent ability to detect variability in severity of post-operative instability symptoms including following shoulder stabilization procedures²⁸.

- The ASES score is designed to assess shoulder function including instability²⁹. It allows for patient self-evaluation through 11 items that can be used to generate a score, divided into 2 areas: pain (1 item) and function (10 items).
- Shoulder Activity Scale is designed to assess patient's shoulder activity level. The activity rating is a numerical sum of scores for five activities rated on a five-point frequency scale from never performed (0 points) to daily (4 points).
- EQ-5D is a standardized measure of health-related quality of life and consists of five dimensions: mobility, self-care, usual activities, pain/discomfort and anxiety/depression.
- VAS Pain Score is used to assess pain on a 100-point scale ranging from 0 to 100, with zero (0) representing no pain and 100 representing the worst pain imaginable.
- Patient Satisfaction will be documented on a visual analogue score of 0-100 "How satisfied are you with your medical care?" Rated by the subject with 0 is the least satisfied, 100 the most satisfied.

Functional outcome assessment will be patient-reported on paper using case report forms administered by the study coordinator or delegate at each site.

4. Physical examination (range of motion and stability): Physical examination following surgery will be performed by the operating surgeon or an assigned delegate and will consist of functional assessment important to patients. Range of motion and shoulder stability are commonly reported outcome measures in the literature when assessing success following shoulder instability surgery^{30,31}. Range of motion will be assessed in forward flexion, abduction, ER and IR. Stability will be assessed primarily via the apprehension- relocation physical examination maneuver which has demonstrated the highest sensitivity in the literature for the diagnosis of anterior instability³². Presence of apprehension will be elicited by bringing the patient's shoulder into a position of 90° of abduction and 90° of external rotation in either the supine or upright position. A positive exam finding is the subjective feeling of impending subluxation or dislocation when in this provocative position. Relocation test is performed, positive test is resolution of feeling of impending subluxation.
5. Return to previous level of activity/sport and work: This outcome will be patient reported at each follow up visit. Time to return to sport will be based on when the patient is cleared by their treating surgeon to return. Time to return to work will reflect duration of work stoppage, if applicable. Specific dates of return to sport/work will be collected on study CRFs.
6. Safety: Rate of major and minor shoulder-related complications and serious adverse events.

Note: Feelings of recurrent instability or re-dislocation, regardless of group allocation and timing of onset, will be considered a treatment failure.

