4.5.1 Arthroscopic Stabilization (Intervention)

Patients randomized to surgical intervention will be required to undergo surgery within 3 months of enrollment. The period of 3 months between enrolment and surgery was chosen to balance practicality in a public system while also seeking to acutely repair the pathology. A focus group of Canadian surgeons was brought together in 2023 and determined this to be reasonable and clinically important. Prior to surgery, advanced imaging will be obtained: MRI, MR arthrogram or preoperative CT scan. This imaging is done as standard care for surgical planning only and will not be used to assess prognosis. For arthroscopic Bankart repair, the participant will be placed in the lateral decubitus or beach chair position. Standard diagnostic arthroscopy will be performed. The capsulolabral complex will be freed from the anterior aspect of the scapular neck. The anterior aspect of the scapular neck will be decorticated using a motorized burr. A capsuloligamentous repair will be performed with the capsule shifted from inferior to superior and repaired on the glenoid face. The number of anchors used for the repair will be left to the discretion of the surgeon (a minimum of 3 anchors recommended). Remplissage procedure will be performed at the

discretion of the operating surgeon. Participants will wear a sling for 6 weeks after surgery. Type of sling will be left to discretion of the treating surgeon. All participants will follow the standardized 3-phase rehabilitation protocol detailed below, starting 6 weeks after surgery once the sling is removed.

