4.5.2 Non-surgical treatment (Control Group)

All participants will follow the standardized 3-phase rehabilitation protocol detailed below immediately after the date of consent, unless the dislocation occurred less than two weeks prior to consent, in which case the patient will wear a sling until they reach two weeks post-dislocation. This is to allow for sufficient healing and pain management prior to initiating physical therapy. Type of sling will be left to discretion of the treating surgeon.

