4.10.1. Follow-Up Visits

Participants will be followed for 24 months post-treatment. All outcome data will be collected at 6 weeks (± 7 days), 6 months (± 30 days), 12 months (± 30 days) and 24 months (± 60 days) post-treatment at regularly scheduled clinic visits. Of note, the first follow-up timepoint (6 weeks) is relative to the initiation of rehabilitation for both groups, i.e. 6 weeks from the date of the first physiotherapy visit. At each time point, participants will complete the WOSI, Shoulder Activity Scale, EQ-5D, VAS pain score, Patient Satisfaction Scale and ASES. Physical examination (PE) will be performed by the operating surgeon or assigned delegate. Shoulder-related adverse events and SAEs will also be documented. In cases where the participant does not return to the clinic or in-person visit is not viable, study personnel will contact the participant by telephone or email. The study questionnaires can be completed by the patient online, through REDCap EDC or by telephone. A missed follow-up form should be completed if the participant misses the follow up visit. An early withdrawal form should only be completed if the participant withdraws their consent. The Schedule of Events (Table 1) details the requirements and procedures for each visit.

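### Post-treatment timing has no common origin in the two arms, so on the plain reading recurrences during the wait for surgery are not in secondary outcome 1

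*Protocol*

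**What the plan says.** **Outcome window.** Protocol Section 4.9, item 1, is "Number of recurrent shoulder dislocations up to 24 months post-treatment". Symptoms of instability carry the same limit, and Section 2.2 repeats both. An end is given, but no start.

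**Visits.** Section 4.10.1 places them at "6 weeks (± 7 days), 6 months (± 30 days), 12 months (± 30 days) and 24 months (± 60 days) post-treatment". It adds that "the first follow-up timepoint (6 weeks) is relative to the initiation of rehabilitation for both groups", meaning the first physiotherapy visit. No anchor is given for the 6-, 12- and 24-month visits.

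**Start of treatment, control arm.** Under Section 4.5.2 rehabilitation starts "immediately after the date of consent, unless the dislocation occurred less than two weeks prior to consent". In that case a sling is worn until two weeks after the dislocation.

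**Start of treatment, surgery arm.** Section 4.5.1 states: "Patients randomized to surgical intervention will be required to undergo surgery within 3 months of enrollment". Rehabilitation follows, "starting 6 weeks after surgery once the sling is removed".

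**Treatment failure.** A note closing Section 4.9 reads: "Feelings of recurrent instability or re-dislocation, regardless of group allocation and timing of onset, will be considered a treatment failure". In Table 1 the row for crossovers and treatment failures is ticked at Visit 1A (surgery) and at Visits 2 to 5. The re-dislocation and instability row is ticked only at Visits 2 to 5.

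**Analysis.** Section 5.2 plans intention-to-treat and per-protocol analyses, with between-group differences and 95% CIs for every secondary outcome at every visit, and no p-values.

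**The concern.** An intention-to-treat comparison needs a clock that starts at the same moment in both arms and does not depend on what happens after allocation. Here the natural start is close to randomisation for controls. For the surgery arm it is a later event, either the operation or the first physiotherapy visit.

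If outcome 1 is read as it stands, a control who re-dislocates in week 8 is counted, and a surgery-arm patient who re-dislocates in week 8 while waiting is not. The surgery arm gives up some months of unoperated risk and gains the same number of months at the far end, after repair. If surgery lowers recurrence, as the rationale in Section 1.4 argues, that exchange flatters surgery.

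The visit comparisons have a related problem. Patients who share a visit label differ in time since randomisation and since injury. Section 2.2 describes these outcomes as the clinical objectives of the definitive trial, so the definitions are likely to carry forward.

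**Working it through.** The protocol gives no figure of its own on this point. The check has three parts.

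**1. Calendar arithmetic, measured from enrolment.** Consent and randomisation are both at Visit 1 in Table 1, so enrolment and randomisation are treated as one date.

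Inputs:
- Control start of rehabilitation (Section 4.5.2): 0 to about 2 weeks, i.e. 0 to 0.46 months.
- Surgery (Section 4.5.1): 0 to 3 months, i.e. 0 to 13 weeks.
- Surgery-arm start of rehabilitation: surgery plus 6 weeks, i.e. 6 to 19 weeks. Since 42 / 30.44 = 1.38, this is 1.4 to 4.4 months.

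Time of visit from enrolment = start of clock + nominal visit time:

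| Visit | Control | Surgery arm, clock from surgery | Surgery arm, clock from rehabilitation |
|---|---|---|---|
| 6 weeks | weeks 6-8 | (anchor stated as rehabilitation) | weeks 12-25 |
| 6 months | 6-6.5 months | 6-9 months | 7.4-10.4 months |
| 12 months | 12-12.5 months | 12-15 months | 13.4-16.4 months |
| 24 months | 24-24.5 months | 24-27 months | 25.4-28.4 months |

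For a patient operated on at 3 months the offset is about 91 days (surgery) or 91 + 42 = 133 days (rehabilitation). Both exceed the ±30- and ±60-day visit windows. The upper ends are not hard limits, because the feasibility threshold in Section 4.8 tolerates 15% of the surgery arm waiting longer than 3 months.

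**2. How many recurrences could fall in the wait (illustration only).**

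Inputs:
- Recurrence r = 42% (Section 1.1) or 47% (Study Summary). Both are given as upper reported rates without a time horizon; 24 months is assumed here.
- Constant hazard in unoperated shoulders: assumed.
- Wait w of 1, 2 or 3 months, the same for everyone: assumed.
- 25 patients in the surgery arm (Section 5.1).

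Share recurring during the wait = 1 - (1 - r)^(w/24).

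| Wait | r = 42% | of 25 | r = 47% | of 25 |
|---|---|---|---|---|
| 1 month | 2.2% | 0.56 | 2.6% | 0.65 |
| 2 months | 4.4% | 1.11 | 5.2% | 1.29 |
| 3 months | 6.6% | 1.65 | 7.6% | 1.91 |

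For example, 1 - 0.58^(3/24) = 0.0658, and 0.0658 × 25 = 1.65. The range is about 0.6 to 1.9 patients. A hazard concentrated in the first months would raise it.

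**3. One event, two classifications.** Take a surgery-arm patient who re-dislocates before the operation. Under the note in Section 4.9 this is a treatment failure, and Table 1 provides for recording it at Visit 1A. Under item 1 of the same section it is not post-treatment if treatment means surgery or rehabilitation. The Table 1 row that feeds item 1 has no tick at Visit 1A. Treatment failure is not among the six listed secondary outcomes, so no listed outcome is shown to include the event as a recurrence.

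**The case against.** The strongest reply is that nothing is lost. The outcome states only an end, so a start at randomisation is not excluded. The note in Section 4.9 covers any instability or re-dislocation whatever the arm and timing, and Table 1 ticks treatment failures at the surgery visit. This stands in part: a reader might infer that pre-surgery events go unrecorded, and the documents do not support that. What remains is that the events are captured under a label that is not a listed outcome.

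Two further inferences are tempting and unsupported. One is that only patients who stay stable reach time zero. No section removes a patient who re-dislocates while waiting, and Section 4.11 keeps non-adherent participants in the study. The other is that surgery-arm patients who opt out have no start date. Section 4.8 has them take up non-operative management, so they would have a first physiotherapy visit.

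It is also fair to say that anchoring the 6-week visit on rehabilitation is deliberate, applies to both arms and aligns patients by stage of recovery. That is reasonable for describing recovery. It does not supply an origin for counting recurrence, or for the later visits.

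Finally, a statistical analysis plan, not at hand, might set the time origin. However, the outcome definition, the treatment-failure note and the Table 1 ticks stand in the protocol and need to agree there.

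**Conclusion.** The point holds as an undefined, arm-dependent time origin and an unreconciled pair of definitions. On the plain reading outcome 1 omits recurrences during the surgical wait, the omission favours surgery, and it conflicts with intention-to-treat.

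The calendar offsets need no assumption beyond the intervals in the protocol, and their upper ends describe a patient who waits the full 3 months. The 0.6 to 1.9 of 25 patients is an illustration. It rests on an assumed 24-month horizon for the 42-47% rates, a constant hazard and an equal wait for everyone.

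Severity is moderate. A reader might infer that the pilot's conclusions are compromised, but its success criteria in Section 4.8 do not use the recurrence count, and Section 5.2 treats the clinical outcomes as exploratory, without p-values. The point still deserves action because the same outcomes are the definitive trial's clinical objectives and the bias has a known direction.

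**What to change.** For the randomised comparison:

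- Define randomisation as time zero for recurrence and instability. Count all events from then to 24 months after randomisation in both arms, including those before surgery. The end needs stating as well as the start: counting up to the 24-month visit would give the surgery arm longer observation.
- State how outcome 1 relates to treatment failure, so that one event has one consistent classification.
- Add a re-dislocation and instability tick at Visit 1A in Table 1.
- State the anchor of the 6-, 12- and 24-month visits, and report the longer patient-reported comparisons with actual time since randomisation. The rehabilitation-anchored 6-week visit may stay as a description of recovery.

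The cost is protocol wording, an event-date field and minor analysis work. No visits are added, since the nominal 24-month visit falls at or after 24 months from randomisation in both arms. A patient seen early in the ±60-day window would be censored at that contact.

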2.2 Secondary Questions

The secondary objectives of the pilot trial will be the clinical objectives of the definitive trial:

1. Rates of recurrent shoulder dislocations up to 24 months' post-treatment;
2. Symptoms of instability without dislocation up to 24 months post treatment;
3. Clinical outcomes measured by Western Ontario Shoulder Instability (WOSI) Index, American Shoulder and Elbow Society (ASES) score, Shoulder Activity Scale, EQ-5D, Visual Analog Scale (VAS) Pain Score, and Patient Satisfaction questionnaire;
4. Physical examination: range of motion, strength, stability;
5. Return to previous level of activity and work, and;
6. Safety, shoulder-related complications and serious adverse events.

Hypothesis: We believe that the pilot trial will be feasible in our ability to recruit participants rapidly and meet our feasibility objectives.

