4.4.1. Blinding

The patient and the study team including the treating surgeon and study coordinator cannot be blinded as they will be undergoing/performing the procedure and/or will have access to post-operative imaging and clinical notes. Outcome assessors and study statisticians, however, will be blinded.

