5.2. Statistical Methods

Primary Analysis (RCT) – Feasibility: We will use descriptive statistics to analyze the primary objective of feasibility of this pilot RCT. The data will be presented as point estimates (proportions and 95% CIs) that define the components of the composite measure of feasibility: recruitment, follow-up, crossovers, and operation within 3 months of enrolment. We will use a “traffic light” approach for feasibility analysis to determine if the definitive trial can proceed or will require any modifications.

Secondary Analysis (RCT): Both intention-to-treat and per protocol analyses will be performed. We will use descriptive statistics to summarize the results. Mean between-group differences and corresponding 95% CIs will be reported for all secondary outcomes at each time point. No p-values will be provided given the trial is not powered for secondary outcomes. These outcomes will be exploratory in nature.

Non-randomized Cohort Analysis: Analysis for the non-randomized cohort will be done in a similar manner to the RCT whereby outcomes will be summarized descriptively by preference of treatment of the patient. Given the small sample size, no formal statistical testing will be performed. Data from the non-randomized cohort will be used to inform feasibility of incorporating a non-randomized cohort within this study design. The same data will be collected for both cohorts but will not be combined.

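### Time to return to sport is set by the unblinded surgeon's clearance, although the outcome is named and described as patient-reported return to the previous level

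*Protocol*

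**What the plan says.** Section 2.2 lists the outcome among the secondary objectives as "Return to previous level of activity and work, and"; the section presents these as the clinical objectives of the later definitive trial.

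Section 4.9, item 5, gives the operational definition in four statements:

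- Source: "This outcome will be patient reported at each follow up visit".
- Timing for sport: "Time to return to sport will be based on when the patient is cleared by their treating surgeon to return".
- Timing for work: "Time to return to work will reflect duration of work stoppage, if applicable".
- Recording: "Specific dates of return to sport/work will be collected on study CRFs".

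On who knows the allocation, Section 4.4.1 says "The patient and the study team including the treating surgeon and study coordinator cannot be blinded", and then "Outcome assessors and study statisticians, however, will be blinded".

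On analysis, Section 5.2 says "Mean between-group differences and corresponding 95% CIs will be reported for all secondary outcomes at each time point". It describes these outcomes as exploratory and plans no p-values for them.

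**The concern.** The name of the outcome and its stated source both point to something the patient does: going back to sport at the earlier level. The timing rule points to something the surgeon does: giving permission. These are different events, and they can fall on different dates or occur one without the other.

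Two things are at stake. First, a difference between arms in time to clearance could reflect how surgeons handle clearance after each treatment rather than how patients recover. The clearing surgeon knows the treatment, and Section 1.4 itself notes that the wish for a quick return to play influences the choice between treatments. Second, the pilot is the place to test definitions. A definition that times permission under the name of return may be carried into the definitive trial unnoticed.

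**Working it through.** No arithmetic applies. The protocol gives no figure for this outcome, so there is nothing to reproduce. The check sets the statements side by side and then follows individual patients through them.

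**Step 1. Which event and which source does each statement use?**

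| Statement | Event | Source |
|---|---|---|
| Name of the outcome (Sections 2.2 and 4.9) | Reaching the previous level again | Not stated in the name |
| Source sentence (4.9, item 5) | Return | Patient |
| Sport timing (4.9, item 5) | Clearance | Treating surgeon |
| Work timing (4.9, item 5) | End of the actual work stoppage | Not stated |
| CRF sentence (4.9, item 5) | Return to sport or work | Not stated |

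Only the sport timing sentence uses clearance. The work sentence shows that timing by the actual event was considered workable in the same item.

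**Step 2. What would each kind of patient contribute?**

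| Patient | Time under the clearance rule | Time under actual return to previous level |
|---|---|---|
| Cleared, and back at the previous level at once | Clearance date | Same date |
| Cleared, back at the previous level later | Clearance date, too early | Later date |
| Cleared, back only at a lower level | Clearance date | None |
| Cleared, never goes back | Clearance date | None |
| Back at the previous level before clearance | Clearance date, too late | Earlier date |

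The two rules agree only in the first row. In the third and fourth rows the clearance rule gives a time to return to sport to a patient who, by the name of the outcome, has not returned.

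**Step 3. Which event will the CRF date record?** The CRF sentence speaks of dates of return. Read alone, that means actual return. Read straight after the timing sentence, it could mean clearance for sport. A site completing the form cannot tell from the protocol.

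**Step 4. Who determines the value?** Section 4.4.1 separates the treating surgeon, who is not blinded, from the outcome assessors, who are. Under the clearance rule the treating surgeon's decision is the data point, so a blinded assessor has no part in it. The patient is also unblinded under the same sentence. Moving to patient report therefore changes what is measured but does not make the measurement blinded.

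**Step 5. Which summary suits the corrected variable?** Under actual return, a patient who has not returned by the last visit has no time, and a mean of times cannot include that patient. A proportion returned by each visit can, because the patient stays in the denominator. It also fits the differences and 95% CIs that Section 5.2 already plans.

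**The case against.** The strongest defence is that item 5 describes two measures that can coexist: whether the patient returned, taken from the patient, and when, taken from the surgeon's clearance. Return status then remains patient reported, and nothing says that a cleared patient who stays away counts as returned. This reading is possible and softens the contradiction. But the text does not state it, and it would still allow a patient with status not returned to carry a time to return to sport. The time variable would remain a time to permission under another name.

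It is also fair to say that the outcome is secondary and exploratory, in a pilot judged on the four feasibility thresholds of Section 4.8. That limits the importance of the point but does not settle the definition.

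Four stronger readings are tempting, and the protocol does not support them:

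- A reader might add up the sling, rehabilitation and surgical waiting periods and infer a fixed gap in clearance time between the arms. No section says that clearance coincides with the end of rehabilitation, the rehabilitation length is only an estimate, and progression depends on criteria. Those periods would also delay actual return, so such a gap would not measure the error and would remain after the fix.
- A reader might infer that non-returners will be dropped and the mean time shortened. Under the clearance rule a cleared non-returner has a time and stays in the mean; only under an actual-return rule is the time missing. Both cannot hold for the same patient. The sentence on mean differences in Section 5.2 is a general one for all secondary outcomes and does not say how non-returners are handled.
- A reader might count the absence of a start date or censoring rule as a defect. Both may properly be left to a SAP, which is not at hand.
- A reader might expect patient report to cure the blinding problem. It does not, because the patient knows the treatment.

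**Conclusion.** The point stands in a limited form. As written, item 5 names patient-reported return to the previous level but times the sport component by the clearance of an unblinded surgeon. It treats work differently, and it leaves open which event the recorded sport date represents. This is a problem of validity: the variable would not measure the outcome it is named after.

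Its reach is one component of one exploratory secondary outcome. No numerical bias can be stated, because the protocol gives neither a rate of non-return nor any relation between clearance and actual return. None of the feasibility criteria depends on it. The conclusion rests on the wording of Sections 4.9 and 4.4.1 and on the plain fact that permission to return differs from returning. It is worth correcting because the change is cheap and the definition is meant to serve the definitive trial. It implies nothing about when a patient should be cleared.

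**What to change.** Reconcile the sentences of item 5 in Section 4.9:

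1. Define time to return to sport as the patient-reported date of actual return to the previous level, using the return dates already planned for the CRFs. Check that the CRF field asks for actual return and for the level reached, and label it accordingly.
2. Count from one common origin in both arms, such as randomisation. This completes the definition; its absence from the protocol is not held as an error.
3. Keep the clearance date, if wanted, as a separate descriptive item under its own name.
4. Report the proportion returned by each visit with the between-group difference and 95% CI, so that patients who have not returned stay in the denominator.

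The cost is a few sentences of protocol text and a CRF label check. If the existing field does not capture actual return and level, one or two fields must be added. The limitation that patient report is also unblinded should be stated alongside the result.
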